#### **4.1.3 Run-in Phase (3 months/up to Day 90)**

As soon as possible after the participant is confirmed to be normokalaemic at the end of the initiation phase (based on local laboratory S-K results from Visits 3b or 3c), the participant will enter the run-in phase (Visit 3d).

Participants will receive open-label SZC and either lisinopril or valsartan. See Section 6.6.2 for instructions on lisinopril/valsartan starting doses. A participant cannot receive both lisinopril and valsartan simultaneously and should not take any other ACEi or ARB concomitantly with lisinopril or valsartan.

The aim of the run-in phase is to increase ACEi or ARB therapy stepwise to their maximum doses using lisinopril or valsartan as per local labels. See Section 6.6 for instructions on dose modification, including monitoring lisinopril/valsartan titration (Section 6.6.1) and management of abnormalities of S-K (Appendix C), lisinopril/valsartan dosing upon entry to and during the run-in phase (Section 6.6.2), strategy for lisinopril/valsartan up-titration during run-in phase visits (Section 6.6.3), and additional unscheduled visits for titration of lisinopril/valsartan (Section 6.6.5).

At the end of the run-in phase (Day 90 [ $\pm$ 3 days], Visit 6a), S-K will be measured by local laboratory. The participant will continue to receive the current prescribed dose of SZC until the S-K result is available. If normokalaemic (S-K  $\geq$  3.5 to  $\leq$  5.0 mmol/L), the participant will proceed to the maintenance phase of the study. If not normokalaemic, the participant will

undergo a follow-up visit at 7 ( $\pm 2$ ) days after the participant's last dose per the SoA (Section 1.3) and exit the study.

**NOTE:** The study is designed to use valsartan as the ARB adjunct to SZC. However, if an actual shortage of valsartan in a local market jeopardises the ability of participants to enter or continue in the study, valsartan can be temporarily substituted with irbesartan until the shortage of valsartan is resolved.

[Appendix E](#) provides conversion information for changing from other ARBs or valsartan to irbesartan, dose equivalence ranges, irbesartan dose modification strategy, and other prescribing information about irbesartan.

During temporary treatment with irbesartan, the same procedures indicated for valsartan discontinuation (Section 7) and efficacy, safety, and other assessments (Section 8) must be followed.

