#### **Adverse Event Variables**

The following variables will be collected for each AE:

- AE (verbatim)
- The date when the AE started and stopped
- Maximum intensity (mild, moderate, or severe). For event of hypokalaemia, mild intensity refers to  $S\text{-}K \geq 3.0$  to  $< 3.5$  mmol/L, moderate intensity  $\geq 2.5$  to  $< 3.0$  mmol/L, and severe intensity  $< 2.5$  mmol/L.
- Whether the AE is serious or not
- Whether the AE required rescue therapy for severe hyperkalaemia or not
- Whether the AE fulfils the criteria of death from kidney failure or not
- Investigator causality rating against each study intervention, SZC, SZC/placebo, and lisinopril/valsartan (yes or no)
- Action taken with regard to each study intervention
- Outcome

In addition, the following variables will be collected for SAEs:

- Date AE met criteria for SAE
- Date investigator became aware of SAE
- AE is serious due to
- Date of hospitalisation
- Date of discharge
- Probable cause of death
- Date of death
- Autopsy performed
- Causality assessment in relation to study procedure(s)
- Causality assessment to other medication

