3.3.1.3 Study Periods

The study consists of five distinct study periods, namely: Screening phase, Initiation phase, Run-In phase, Maintenance phase and Follow-Up phase. Participants will transfer directly between study periods in the order given.

The five phases are delimited in time like this:

Screening phase

- *First day*: the day of the date of signature on the signed informed-consent form (ICF).
- *Last day* (if participant not going into Intervention period/Initiation phase): the day of last contact.
- *Last day* (if participant going into Intervention period/Initiation phase): the day before first Initiation-phase S2C-dose.

Note: If there is no signed ICF, then there is no Screening phase, and no other phases either.

Initiation phase

- *First day*: the day of first Initiation-phase S2C-dose.
- *Last day* (if not going into Run-in phase): the day of last Initiation-phase S2C-dose.
- *Last day* (if going into Run-in phase): the day before the first day of the Run-in phase (see below).

Run-in phase

- *First day*: the day of first Run-in SZC dose, or the day of first Run-in (IP) RAASI-dose, whichever comes first, however no earlier than the day after last Initiation-phase SZC-dose.
A consequence of this is that the Run-in phase always has its first day on the day after last Initiation-SZC dose, *at the earliest*; if any Run-in IP (SZC, lisinopril, valsartan, irbesartan), would be initiated before, or on the same day as, the last Initiation SZC dose, then the Run-in phase will start on the day after the day of last Initiation-SZC dose. This means that any Initiation-SZC dosing takes precedence over any Run-in IP dosing when it comes to separating the Initiation phase and the Run-in phase, in favour of the Initiation phase. If – on the other hand – both Run-in SZC and Run-in RAASI would start on a day (potentially different days for Run-SZC and Run-in RAASI) *after* the day of last Initiation SZC then the Run-in phase will have its first day on the day of the earliest initiation of any of the two Run-in IP types (SZC or RAASI). This means that any time “gap” between Initiation SZC and Run-in IP will be assigned to the Initiation phase.
- *Last day* (if not going into Maintenance phase): the day of last Run-in SZC-dose, or the day of last Run-in (IP) RAASI-dose, whichever comes last.
- *Last day* (if going into Maintenance phase): the day before the day of randomisation.

Maintenance phase

- *First day*: the day of randomisation.

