- *Last day*: the day of last contact.

Note: No Follow-up phase will follow the Maintenance phase.

Follow-up phase

- *First day*: The day after last day of the immediately preceding phase (Initiation phase or Run-in phase; no Follow-up phase will follow the Maintenance phase and the Screening phase; see above). However, if the day of last contact would occur in a preceding phase, then there will not be any Follow-up phase.
- *Last day*: The day of last contact.

Note 1: A Follow-up phase can only occur following the end of the Initiation phase or following the end of the Run-in phase. No Follow-up phase will occur after the Maintenance phase.

Note 2: There will not be any Follow-up phase if the day of last contact would occur in a preceding phase.

For the purpose of presentation of **safety analyses**, the follow up phase will generally be combined with the phase that directly precedes it.

For the purpose of presentation of **patient disposition**, the study periods as provided by the investigator (such an option exists in the CRF for disposition events in particular) will be used.

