3.3.1.4 On-treatment and During Period definitions

An event, or measurement, is said to be occurring during a particular period if the start date of the event, or the date of measurement, falls within the start and end date of the period as defined in Section 3.3.1.3.

An event, or measurement, is said to be occurring on-treatment for a particular period if the start date of the event, or date of measurement, falls within this period and simultaneously occurs between the first dose date and last dose date of SZC/Placebo, for that period, plus one day.

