4.5 Safety Analyses

The domain safety covers exposure, adverse events, clinical laboratory, vital signs, and ECG.

Tables will be provided for the safety sets, listings are provided for all enrolled subjects, or the safety sets, depending on the availability of data. For the tabular summaries, subjects that erroneously received incorrect IP during the maintenance phase of the study (SZC or Placebo) will be analysed as belonging to the treatment group they were randomized to.

As a rule, safety analysis will be presented for both On Treatment and During Study. Further, as a rule, the safety analyses will be presented separately for different phases, with events occurring during follow-up assigned to the study phase directly preceding the follow-up period.

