4.5.1.2 Presentations

Adverse events (AE) will be summarised descriptively in accordance with the rules described in Section 3.3. Estimates of differences in AE profiles (e.g., hazard ratios, difference in probability of an event occurring within a pre-specified time interval) may also be presented, along with the corresponding CIs.

All AEs will be summarised by SOC and PT according to the latest MedDRA version available at the time of database lock.

Overall overview

An AE overview table will be created, with AEs falling within the following categories summarized by treatment group.

- Any AE
- Any SAE

- Any AE with outcome death
- Any AE leading to discontinuation of SZC or SZC/placebo
- Any AE leading to discontinuation of Lisinopril/valsartan
- Any AE leading to dose interruption of SZC or SZC/placebo
- Any AE leading to dose interruption of Lisinopril/valsartan
- Any AE leading to dose reduction of SZC or SZC/placebo
- Any AE leading to dose reduction Lisinopril/valsartan
- Any AE possibly related to SZC or SZC/placebo
- Any AE possibly related to Lisinopril/valsartan
- Any SAE possibly related to Lisinopril/valsartan
- Any SAE possibly related to SZC or SZC/Placebo

AEs, SAEs, DAEs and deaths, by system organ class and preferred term

A detailed overview of number, and percentage, of subjects with AEs, SAEs, DAEs and deaths in a particular SOC and PT class will be presented.

Most common AEs

A tabulation of the PT terms sorted by decreasing frequency (most common AEs in SZC arm on top) will be provided.

Intensity of AEs

An overview of the number and the percentage of subjects with AEs in a particular SOC, PT and intensity class (mild, moderate, severe) will be created. Subjects will be counted only once in each category. A subject with two AE in the same SOC and PT class of, e.g., both high and moderate intensity will be assigned the “high” intensity category, i.e., the more severe class.

Causality of AEs

Number and percentage of subjects with AEs considered as possibly related to each of the IPs (SZC/Placebo and Lisinopril/valsartan) will be tabulated by SOC and PT, in separate tabulations.

Events related to oedema, hypokalaemia, or hyperkalaemia

An overview of oedema-related AEs, with number and percentage of subjects with an event with a particular PT term, will be presented.

Number of subjects with AE classified as hypokalaemia, hyperkalaemia, or hyperkalaemia requiring rescue, will be tabulated in a similar manner.

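### An AE recorded once that starts in the open-label run-in and turns serious, fatal or drug-stopping after randomisation is missing from the by-arm maintenance AE counts

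*SAP*

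**What the plan says.** - **Split by phase.** SAP 4.5 states that, as a rule, "the safety analyses will be presented separately for different phases, with events occurring during follow-up assigned to the study phase directly preceding" it. Protocol 9.4.3 likewise plans safety summaries by arm and phase.
- **Allocation rule.** SAP 3.3.1.4: "An event, or measurement, is said to be occurring during a particular period if the start date of the event" lies between the first and last day of that period. To be on-treatment, the start date must be one that "falls within this period and simultaneously occurs between the first dose date and last dose date of SZC/Placebo, for that period, plus one day". Both definitions depend on onset.
- **Boundary.** Under SAP 3.3.1.3 the run-in of a participant who goes on to maintenance ends on "the day before the day of randomisation", and maintenance starts on the day of randomisation. There are no arms before that point. Protocol 4.1.3 says of the run-in: "Participants will receive open-label SZC and either lisinopril or valsartan".
- **Tables affected.** SAP 4.5.1.2 gives an overview table (SAEs, fatal AEs, and AEs leading to discontinuation, interruption or dose reduction of either product) and "A detailed overview of number, and percentage, of subjects with AEs, SAEs, DAEs and deaths in a particular SOC and PT class". Neither has a date rule of its own.
- **Dates collected.** The AE variables in Protocol 8.3.2 include "Date AE met criteria for SAE" and the date of death. Protocol 7.1.1.1 and 7.1.2 record the times of permanent and temporary discontinuation.
- **Disposition.** SAP 3.3.1.3 takes a different route: "the study periods as provided by the investigator (such an option exists in the CRF for disposition events in particular) will be used".

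**The concern.** The maintenance phase is the trial's only controlled safety comparison, and everyone who enters it has had about three months of SZC with lisinopril/valsartan up-titration. AEs ongoing at randomisation are therefore to be expected. Some could reach their important outcome, such as hospitalisation, death or a stop of SZC/placebo, under randomised treatment. With onset as the only criterion, that outcome is credited to a phase with no comparator. The by-arm counts of SAEs, deaths and discontinuations are then incomplete for outcomes that occurred after randomisation. The run-in tables also take in outcomes that did not occur in the run-in.

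**Working it through.** The plan states no figure for AEs that cross randomisation, so no arithmetic applies. The check is to apply the written rules to one case.

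**Case.** An AE starts on study day 60, in the run-in. The participant is randomised at about day 90. On maintenance day 30 the AE becomes serious, proves fatal or leads to stopping SZC/placebo. The site keeps one AE record with its original start date.

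1. *During maintenance?* The start date (day 60) precedes the first day of maintenance (about day 90). No.
2. *On-treatment in maintenance?* The start date must first fall in the period. No.
3. *During run-in?* Day 60 precedes the last run-in day. Yes.
4. *Does a carry-over rule move it?* The only one, in SAP 3.3.1.3 and 4.5, assigns follow-up events backwards to the preceding phase. Nothing moves an event forward, and no follow-up phase comes after maintenance. No.
5. *Does the table have its own date?* SAP 4.5.1.2 gives none. SAP 4.5.1.1 derives times to seriousness, death and discontinuation of IP, but as duration variables for presentations such as key subject information, not for placing events in phases. No.

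Result: the event counts once in the single-arm run-in tables and contributes zero to the SZC-versus-placebo count of SAEs, deaths or AEs leading to discontinuation. AEs leading to interruption or dose reduction follow the same path.

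**Can one record span the boundary?** Protocol 8.3.2 lists, per AE, a start and a stop date, a single maximum intensity, seriousness, action taken and outcome. The date on which SAE criteria were met is separate from the start date. Causality is rated separately for SZC and for SZC/placebo. The form can therefore hold an AE that began on open-label SZC and later led to action on the randomised product.

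**Consistency with disposition.** Protocol 7.1.1.1 requires participants who permanently stop either product in the run-in to stop the other and leave the study, apart from a permitted lisinopril-to-valsartan switch. SAP 4.1.1.1 accordingly expects completion of run-in treatment to coincide with completion of the phase. Under the onset rule, the run-in table of AEs leading to discontinuation can nevertheless include people who completed the run-in, were randomised and stopped later.

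**The case against.** The strongest reply is that little is lost from the report. Disposition is tabulated by arm in maintenance (SAP 4.1 and 4.1.1.2), covers phase and treatment discontinuation, and uses the investigator's period. Key subject information is planned for all SAEs, fatal AEs and AEs leading to IP discontinuation. Listings cover the whole study and show planned arm. This stands, and it limits the gap to the comparative AE count tables. Individual listings do not replace by-arm counts, however, and disposition does not cover SAEs, interruptions or reductions.

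A second reply is that worsening may be recorded as a new AE. Protocol Appendix G 1 lets an AE include deterioration of an existing condition, and Protocol 8.3.5 has aggravated examination findings reported as AEs. A new record with a post-randomisation start date would be counted by arm. This also stands, but nothing requires a new record, so the count depends on site practice.

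Third, onset-based allocation is a defensible principle: it confines the comparison to AEs arising after randomisation. Moving every SAE off its onset date would charge the placebo arm with events that began on open-label SZC. That argues against wholesale re-allocation and for a supplementary table.

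Fourth, disposition and AE tables may show different numbers of deaths, but SAP 3.3.1.3 openly uses different period definitions for them, so this is not in itself a defect. Finally, the words *as a rule* in SAP 4.5 leave room for exceptions, but none is defined.

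**Conclusion.** The point holds as a fault in a stated rule. It assumes that the AE is kept as one record with its original start date and that no undocumented exception to SAP 3.3.1.4 is applied. It concerns AEs with complete dates. Its size is not known: the documents give no count of AEs spanning randomisation.

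Three stronger readings are tempting and are not supported.

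- **That these events disappear or that harm is hidden.** They stay visible in the listings, key subject information and, for deaths and treatment stops, disposition.
- **That the omissions fall mainly on the SZC arm.** This assumes that the carried-over AEs are caused by SZC and resolve on withdrawal. That is plausible for some oedema, but the documents do not show it for AEs in general. AEs unrelated to treatment would be expected to balance by randomisation, and events tied to RAASi or hyperkalaemia may behave differently. The run-in exit rule also shrinks the carried-over pool.
- **That a number can be given.** One could start from 0.057 x 1360 = 78 oedema cases (Protocol Table 3) or 0.06 x 1360 = 82 deaths (Protocol 9.2) and take a share. But 5.7% is a figure from the SZC clinical trials, not a three-month onset rate. The 6% is a two-year planning value. The 1360 is a target for a study that ended prematurely (SAP amendment history). The shares ongoing at randomisation and later progressing appear nowhere in the documents.

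**What to change.** In SAP 4.5.1.2:

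1. Keep start-date allocation for the all-AE tables.
2. Count deaths in the maintenance tables by date of death.
3. Add one supplementary by-arm table of AEs with onset before randomisation for which any of these dates is on or after randomisation: SAE criteria met, death, or discontinuation, interruption or dose reduction of IP.
4. Cross-refer to this from SAP 3.3.1.4, so that the onset rule is not read as the only one.

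Cost: a short paragraph of SAP text and limited programming on data already collected. The AE variables in Protocol 8.3.2 list the action taken but not its date, so dates of interruption and reduction must come from the dosing records (Protocol 6.4 and 7.1.2) and be matched to the AE.

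Downside: an AE can appear in both a run-in and a maintenance table, and some events that began on open-label SZC will be shown under placebo. A footnote giving the onset phase is needed.

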4.5.2 Clinical Laboratory, Blood Sample

Clinical Laboratory results will be summarised descriptively in accordance with the rules described in Section 3.3. The definition of baseline is found in Section 3.3.1.1.

4.5.2.1 Definitions and Derivations

Abnormalities

Abnormal values will be determined by comparing the lab values to standard ranges, as provided by the central laboratory.

Hypokalaemia and Hyperkalaemia

Potassium values will be used to summarise patients who are Hypokalaemic ($S-K < 3.5$ mmol/L) or Hyperkalaemic ($S-K > 5.0$ mmol/L), with the following sub-categories also being presented:

Hypokalaemia:

- $S-K < 3.5$ mmol/L
- $S-K < 3.0$ mmol/L
- $S-K < 2.5$ mmol/L

Hyperkalaemia:

- $S-K > 5$ mmol/L
- $S-K > 5.5$ mmol/L

- S-K > 6.0 mmol/L
- S-K > 6.5 mmol/L

4.5.2.2 Presentations

Haematology and Clinical Chemistry

Hematology results, collected at Screening Visit and Randomization, will be summarized descriptively in accordance with the rules described in Section 3.3. The values collected at Screening Visit could further be summarised by hyperkalaemia status (screening SK > 5 mmol/L, Yes/No).

A summary of the distribution of haematology and clinical chemistry profiles during the maintenance phase, over time, will be provided, the presentation including a summary of the values themselves, by visit, and change from baseline, also by visit.

The number, and percentage, of patients with abnormal haematology and clinical chemistry values at any point during the maintenance phase, but with normal baseline (pre-randomization) values, will be presented.

Hypokalaemia and Hyperkalaemia

The number of subjects who were Hypokalaemic or Hyperkalaemic at any point in the study will be summarised according to the categorization provided above. This may be complemented by a presentation of the number of subjects who were Hypokalaemic or Hyperkalaemic at each visit.

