#### **2.2.3.2 Increased Serum Bicarbonate**

SZC has also been found to consistently raise serum bicarbonate and this effect is likely to be due to ammonium binding and elimination in the gut by SZC (Ash et al 2015, Roger et al 2020). The observed increase in bicarbonate is a potential mechanism for nephroprotection by ameliorating acidosis, which is common in patients with CKD. Metabolic acidosis has been shown to be linked to CKD progression (Shah et al 2009) and bicarbonate therapy may slow its progression (Di Iorio et al 2019). Bicarbonate therapy has been suggested to provide kidney benefit to patients without overt acidosis (Mahajan et al 2010).

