#### **4.2.1 Rationale for the Study Population**

The population included in this study comprises patients with moderate to severe CKD (eGFR  $\geq 25$  to  $\leq 59$  mL/min/1.73m^2) and albuminuria (UACR  $\geq 200$  and  $\leq 5000$  mg/g) with

hyperkalaemia or at risk of hyperkalaemia. The presence of a reduced eGFR together with significant albuminuria ensures that the selected population is at risk of progression of CKD and can potentially benefit from the proposed mechanisms of action of SZC. RAASi therapy, eg, ACEi/ARB treatment, is renoprotective and slows progression in early and advanced CKD patients. The low eGFR cut-off value is set at 25 mL/min/1.73m^2 to avoid enrolling patients with more advanced CKD who are at risk for rapid progression to ESKD, and who commonly cannot tolerate maximal ACEi/ARB doses because of the risk of further haemodynamic kidney impairment. In addition, including patients with very advanced kidney disease would detract from the ability to obtain meaningful long term eGFR slope data. Hyperkalaemia is a common reason for down-titration or discontinuation of ACEi/ARB therapy and constitutes the main barrier to attaining optimal therapy. SZC is likely to benefit this population by enabling optimisation of ACEi/ARB therapy in hyperkalaemic patients, and in patients at high risk of hyperkalaemia upon ACEi/ARB up-titration.

As indicated in Section 2.2.3, SZC may exert renoprotective effects in the proposed study population independently of ACEi/ARB optimisation (bicarbonate rise and potassium/aldosterone reduction). To study the effects of all potential SZC mechanisms of action, the proposed study patient population will include 2 subgroups of approximately equal size, based on S-K and RAASi therapy criteria, as follows:

- Hyperkalaemia and on adequate or limited RAASi therapy due to hyperkalaemia
- Normokalaemia and on limited RAASi therapy due to high risk of hyperkalaemia

The mechanisms underlying the potential benefit of SZC are relevant in all 2 subgroups (RAASi optimisation, acidosis correction, hyperkalaemia amelioration, and aldosterone reduction). The study population defined by the above eligibility criteria and study subgroups is considered well representative of a CKD population at risk of progression that is likely to benefit from treatment with SZC.

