##### **Type of Participant and Disease Characteristics**

- 3 Must have eGFR  $\geq 25$  and  $\leq 59$  mL/min/1.73m^2 as calculated by central laboratory (CKD-EPI formula; [Delgado et al 2022](#), [Inker et al 2021](#)) at screening (Visit 1).
- 4 Must have UACR  $\geq 200$  and  $\leq 5000$  mg/g as calculated by central laboratory at screening (Visit 1). If the first sample does not fulfil eligibility criteria, a second sample can be

obtained during the screening period; if so, the UACR measurement from the second sample must be within the eligibility range.

5 Any of the following criteria, a or b, at screening (Visit 1):

- (a) Cohort A: Hyperkalaemia ( $S\text{-}K > 5.0$  to  $\leq 6.5$  mmol/L) as measured by the central laboratory, and on adequate\* or limited\*\* RAASi therapy due to hyperkalaemia.
- (b) Cohort B: Normokalaemia ( $S\text{-}K \geq 3.5$  to  $\leq 5.0$  mmol/L) as measured by the central laboratory and on limited\*\* RAASi therapy due to high risk of hyperkalaemia. High risk of hyperkalaemia is defined as:
  - (i) Participants with a previous medical history or record of hyperkalaemia within the prior 24 months, who are on limited\*\* RAASi therapy despite indication in CKD.
  - (ii) Participants in whom RAASi therapy is indicated in CKD, who are on limited\*\* RAASi therapy and have  $S\text{-}K \geq 4.7$  to  $\leq 5.0$  mmol/L.
  - (iii) Participants in whom RAASi therapy has been discontinued or reduced to suboptimal\* doses because of hyperkalaemia.

\*Adequate RAASi dose levels are defined in Appendix B 3; doses lower than these are considered as suboptimal.

\*\*Limited RAASi therapy is defined as no or suboptimal RAASi therapy according to dosing guidance provided in Appendix B 3.

6 If on thiazide or loop diuretics, the dose must have been stable for 2 weeks prior to screening (Visit 1).

7 If on RAASi therapy, the dose must have been stable for one month prior to screening (Visit 1) and remain stable during screening.

8 If on an SGLT2 inhibitor (ie, dapagliflozin and canagliflozin), finerenone, or any other medications in these 2 classes that are approved for CKD, the dose must have been stable for 3 months prior to screening (Visit 1).

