**Table 9 Laboratory Efficacy Variables**

Primary endpoint	Secondary endpoint

• eGFRa (S-Creatinine)

	

• eGFRa (S-Creatinine)

• UACRb (U-Albumin and U-Creatinine)

• S-Potassium

• S-Bicarbonate

a The eGFR will be derived by race agnostic CKD-EPI equation (Delgado et al 2022, Inker et al 2021) and calculated by central laboratory for the analysis of the primary endpoint. The race adjusted eGFR will also be calculated and may be used for sensitivity or supportive analyses (Levey et al 2009).

b The UACR will be calculated by central laboratory.

CKD-EPI, Chronic Kidney Disease Epidemiology Collaboration; eGFR, estimated glomerular filtration rate; S, serum; U, urine; UACR, urine albumin-to-creatinine ratio.

Analyses will be performed at a central laboratory contracted by AstraZeneca; the timing of the samples is indicated in the SoA (Section 1.3). For instructions on the sampling process, see Section 8.2.4.1.

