#### **Vital Signs, Laboratory Evaluations, and ECG**

The distribution of the measurements over time will be illustrated by presenting the summary statistics (mean, SD, median, minimum, maximum) of the values obtained at the study visits, as well as change from baseline to each of the respective visits. The occurrence of extreme measurements, eg, measurements falling outside pre-defined criteria at any point during a study phase, or measurements judged to be abnormal by the investigator, will be summarised by means of frequencies and percentages.

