| Section 7 Appendix | 01 Dec 2022 | Creation of Appendix 7.2 The assignment of countries to regions. A mapping of countries to regions has been added. | Yes | For programming purposes. |
| Section 7 Appendix | 01 Dec 2022 | Creation of Appendix 7.2 Sample size calculation. | Yes | The sample size calculation present in CSP has been added to the SAP for readers convenience. |
| Section 3.3.1.2 | 22 Jan 2023 | Definition of phases updated | Yes | To accommodate some specific cases observed in the (blinded) data during dry run preparation. |
| Section 4.2 | 22 Jan 2024 | Deletion of a large part of supplementary and sensitivity analyses. | Yes | Due to the premature termination of the study, the decision was taken to slim down the scope of the CSR. All the main analyses remain as previously defined. However, majority of supportive and supplementary analyses have been removed as superfluous in view of the limited data availability. |
| Section 4.2 | 24 Apr 2024 | Simplification of the data exploration | Yes | For the same reason as above, even other simplifications have been introduced. For instance, no extensive exploration of missing data patterns will be performed. Some sub-group analyses have been removed. |
| Section 4.2.1.5 | 24 Apr 2024 | Minor change in sub-group analysis approach | Yes | The effect estimates will now be obtained for each sub-group separately, rather than from a global model via application of contrasts. Changed for simplicity of implementation. |

| | | | | |
|-------------|-------------|--|--|--|
| Section 4.2 | 24 Apr 2024 | Exclusion of the late measurements | No | Due to the termination of the study, the number of laboratory measurements later in the study is very limited. As such, all the lab-based analyses (majority of efficacy) will be performed on data obtained up to and including visit 17. |
| 4.2.6 | 24 Apr 2024 | Change of the repeated measurements analysis from mixed model to GEE | Yes | Relative ease of interpretation, as GEE works with marginal odds, rather than conditional ones, leading to a closer correspondence to a simple number (%) type of tabulation. |
| 4.5 | 24 Apr 2024 | Actual treatment removed from listings | Yes | |
| 4.5.1 | 24 Apr 2024 | All AEs resented by PT in decreasing frequency, rather than only the most common ones. Sorting now by SZC. | Yes | |
| 4.5.2 | 24 Apr 2024 | For all abnormality tabulations, only patients with normal values at baseline are included. | Yes | |

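### The laboratory abnormality table counts only participants normal at the pre-randomisation baseline, whatever the direction, and no shift table covers those who start outside the range

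*SAP*

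**What the plan says.** SAP 4.5.2.2 (Haematology and Clinical Chemistry) presents the number and percentage of participants with an abnormal value at any time in the maintenance phase, "but with normal baseline (pre-randomization) values, will be presented". The SAP amendment history has a matching entry for Section 4.5.2, dated 24 April 2024: "For all abnormality tabulations, only patients with normal values at baseline are included". That entry is marked as in line with the protocol and gives no rationale. Abnormality is defined in SAP 4.5.2.1: "Abnormal values will be determined by comparing the lab values to standard ranges, as provided by the central laboratory". Neither document prints those ranges.

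Protocol 9.4.3 (Vital Signs, Laboratory Evaluations, and ECG) describes the display differently: "The occurrence of extreme measurements, eg, measurements falling outside pre-defined criteria at any point during a study phase" is to be summarised by frequencies and percentages. No condition on the baseline value is stated.

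For vital signs, SAP 4.5.3.2 plans a comparison of abnormality status at baseline with status at the minimum or maximum value. No equivalent is planned for laboratory values.

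**The concern.** The filter takes no account of direction. A participant low at baseline cannot be counted as newly high, and a participant high at baseline cannot be counted as newly low. A participant already outside the range who moves further out is not counted either.

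This matters more here than in a trial of people with normal laboratory values. Inclusion criterion 3 requires an eGFR of 25 to 59, and eGFR is computed from serum creatinine (Protocol Table 9: "The eGFR will be derived by race agnostic CKD-EPI equation"). Creatinine, urea nitrogen and bicarbonate are all central laboratory safety variables in Protocol Table 10. The entry criteria therefore push at least creatinine, and probably urea, towards an abnormal baseline. Bicarbonate is of interest because the protocol states that acidosis is common in CKD and that "SZC has also been found to consistently raise serum bicarbonate".

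At stake is whether the safety report can show how many participants in each arm moved to a new or opposite abnormality, given where they started.

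**Working it through.** The plan states no figure for this table, so there is nothing to reproduce. The check has three parts.

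**1. Who is counted under the current rule**

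| Baseline to worst value in maintenance | Counted in SAP 4.5.2.2? |
|---|---|
| normal to high, normal to low | yes |
| low to high, high to low | no |
| high to higher, low to lower | no |
| missing to any abnormal value | no, read literally |

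The last row should be rare. Central chemistry is scheduled at randomisation, and SAP 3.3.1.1 allows a 5-day look-back for the maintenance baseline.

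**2. Whether another output fills the gap**

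- By-visit summaries (SAP 4.5.2.2 under the rules of 3.3) have no baseline filter and include minimum and maximum. They do not count participants or tie an extreme to baseline status. SAP 3.3.3 removes unscheduled values from them and names out-of-range tabulations as a place where unscheduled values belong.
- The eGFR analyses (SAP 4.2.1 and 4.2.2) follow creatinine, and the composite counts sustained declines of at least 40% or 50% from randomisation. They do not cover urea or the other analytes.
- The bicarbonate responder display (SAP 4.2.5.2) treats every value above 22 mmol/L as normal, so a move from low to above the upper limit appears there as normal.
- Potassium has its own threshold table in SAP 4.5.2.2, with no baseline condition in that paragraph.
- Adverse events (Protocol 8.3.5) include laboratory deterioration if it is serious, leads to discontinuation or is judged clinically relevant, whatever the baseline.

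None of these gives participants by baseline class and worst value.

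**3. Size, on assumption**

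The share p out of range at baseline cannot be derived from the documents. The reference limits are not given, and the filter applies at randomisation, about 3 months after the screening eGFR. I therefore show a range of p. The planned number per arm is 1360 / 2 = 680. Participants able to appear in a row number 680 × (1 − p). If 10% of those become abnormal (illustrative), the count is 0.10 × 680 × (1 − p).

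| p (assumed) | can appear | cannot appear | count at 10% | as % of 680 | as % of those normal at baseline |
|---|---|---|---|---|---|
| 30% | 476 | 204 | 48 | 7.0% | 10% |
| 50% | 340 | 340 | 34 | 5.0% | 10% |
| 70% | 204 | 476 | 20 | 3.0% | 10% |
| 90% | 68 | 612 | 7 | 1.0% | 10% |

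The last two columns matter because SAP 3.3 lets the denominator depend on the analysis and 4.5.2.2 does not fix it. The same data can read as 1% or 10%. The study closed early, so actual counts will be smaller; the proportions carry over.

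**The case against.** Restricting to a normal baseline is a usual way to show newly arising abnormality, and it was chosen deliberately. Protocol 9.4.3 gives its criteria only as an example and leaves them to be defined, so the SAP may fill them in this way. That stands: this is a narrowing of an open plan. A reader might infer that the protocol promised a count in every participant, but it only states no restriction.

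A reader might also infer that the safety report cannot see kidney deterioration or individual extremes. The documents do not support that. Minimum and maximum are shown by visit for everyone, kidney function has the co-primary endpoints and the composite, and clinically relevant deterioration is reportable as an adverse event.

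The bicarbonate argument is weaker than it first looks. The maintenance baseline follows about 3 months of open-label SZC, and the SZC arm starts maintenance at its last run-in dose. Much of any rise should precede baseline, and the change expected after randomisation is mainly a fall on placebo, which the table does count when it goes from normal to low. Low to high remains possible, but the documents give no basis for calling it frequent.

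For creatinine, an out-of-range flag says little in this population, with or without the filter. This also stands, and it limits what the fix can recover.

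**Conclusion.** The point holds as a minor gap in a descriptive safety display. The rule leaves out everyone already abnormal, regardless of direction, and no other planned output counts participants by baseline class and worst value or brings in their unscheduled extremes. No efficacy result or test is affected.

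That many participants start with creatinine above range is an inference from the entry criterion and the creatinine-based eGFR. For urea it is a matter of direction only. It is tempting to say that most participants drop out of both rows, but without reference ranges or baseline distributions the documents cannot establish that share. The 30% to 90% range above is an assumption used to show scale. The set concerned is the maintenance safety set (SAS-MP), since SAP 4.5 bases safety tables on the safety sets.

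**What to change.** In SAP 4.5.2.2:

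- Make the rule direction-specific: newly high among participants not high at baseline, and newly low among those not low at baseline. State those groups as the denominators.
- Add one shift table for all SAS-MP participants with a post-baseline result: baseline class (low, normal, high, missing) by worst low and worst high maintenance value, with unscheduled values included.
- State whether the amendment entry on all abnormality tabulations applies to the potassium threshold table, whose own paragraph has no such condition.

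One limit remains. A class-based shift table puts a participant who stays high and one who rises further in the same cell. Separating them would need a change-based criterion, which is for the clinical team to choose.

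The cost is a few sentences and one table shell on data already collected. The drawback is one more table in a report deliberately shortened after early termination.
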